# 9.2.2.2 Primary analysis

The primary analysis will be performed on the FAS. Measurements obtained after premature treatment discontinuation will be excluded from the analysis, leading to a hypothetical strategy estimand [the primary estimand, Table 4]. This estimand addresses the full potential of ACT-539313 which is most relevant for this type of study.

Changes from baseline to post-baseline time points in the number of BE days per week will be analyzed using a mixed model for repeated measurements with factors for treatment group, sex, BMI category ( $< 30 \text{ vs} \ge 30 \text{ kg/m}^2$ ) and time point (Weeks 1–2, 3–4, 5–6, 7–8, 9–10, and 11–12), treatment by time interaction and covariates for baseline number of BE days per week and the interaction between baseline and time point.

An unstructured covariance matrix will be used to account for the correlation between repeated measurements from the same study participant. If this analysis fails to converge, the following structures will be tested in a subsequent order until model-convergence is achieved: heterogeneous Toeplitz; Toeplitz; autoregressive; compound symmetry. The Kenward-Roger approximation will be used to estimate denominator degrees of freedom.

A restricted maximum likelihood approach in combination with the Newton Raphson Algorithm will be used.

LSMeans for each treatment group and time point will be obtained from the mixed model. The null hypothesis associated with the primary endpoint is that there is no difference between ACT-539313 and placebo in the mean change from baseline to Week 11–12 in the number of BE days per week. This hypothesis will be tested at a two-sided significance level of 5% based on the (ACT-539313 minus placebo) difference in LSMeans at Weeks 11–12. The null hypothesis will be rejected if the 95% CI around this difference excludes zero.

Mean changes from baseline in the number of BE days per week by treatment group will be displayed graphically to illustrate the time course of the primary endpoint.

# 9.2.2.3 Handling of missing data and intercurrent events

All efforts will be implemented to minimize the amount of missing data. Visits are performed at regular and short intervals for the investigator to closely follow-up with the diary completion.

The primary efficacy analysis assumes a missing at random mechanism (i.e., missingness is conditionally independent from the unobserved values of the primary endpoint, given the covariates in the mixed model).

*Potential impact of COVID-19 pandemic on statistical analyses.* The COVID-19 pandemic may lead to missed or postponed visits, but the study participant's binge eating diaries can still be evaluated at the next visit to collect the information for the primary endpoint [see Section 7.2.5.8]. Any missing diary data due to the COVID-19 pandemic is considered missing completely at random and satisfies the assumption underlying the main analysis (linear mixed-effects model, assuming missing at random).

# 9.2.2.4 Sensitivity analyses

Sensitivity analyses will be performed assuming a missing not at random mechanism, where missingness is related to the unobserved value of the endpoint. The model will utilize a multiple imputations approach based on a control-based imputation, which assumes that missing values of study participants in the ACT-539313 group are similar to observed values of study participants in the placebo group.

These sensitivity analyses will be described in the SAP.

# 9.2.2.5 Supplementary analyses

The same analysis will be performed on the PPS [supplementary estimand #2, Table 4].

# 9.2.2.6 Subgroup analyses

The aim of the subgroup analyses is to explore the consistency of the treatment effect across the following subgroups:

- Age (18–29 vs 30–55 years)
- Sex (male vs female)
- Race (Black, Caucasian, other)
- BMI ( $< 30 \text{ vs} \ge 30 \text{ kg/m}^2$ )

Results of the subgroup analyses will be displayed in a forest plot displaying treatment effects per subgroup and their 95% CIs (obtained by conducting the primary analysis by subgroup) with vertical reference lines at no effect as well as at the overall treatment effect. P-values for treatment by subgroup interaction will be provided for exploratory purposes, based on the primary analysis model extended with treatment by time and by subgroup interaction.

# 9.2.3 Analysis of the secondary efficacy outcome(s)

Not applicable.

# 9.2.4 Analysis of exploratory efficacy outcomes

Only the analyses of select exploratory endpoints [Table 2] are described here. The analyses of endpoints associated other objectives will be described in the SAP.

# 9.2.4.1 Variable definitions

- Changes from baseline up to Weeks 11–12 in the number of BE episodes per week based on diary data, defined based on the 2-week intervals defined for the primary endpoint. The number of BE episodes per week is defined as the number of BE episodes in the applicable 14-day time interval divided by the total number of diary days, times 7.
- Absence of BE episodes during the last 4 weeks of the treatment period, defined as no BE episodes during study days 57–84. A minimum of 4 out of 7 diary entries are required for days 57–63, 64–70,71-77 and 78–84, otherwise the outcome will be set to 'No absence'.
- Change from baseline to Week 12 in EDE-Q7 global score, defined as the difference of EDE-Q7 global score at Week 12 and at Baseline. Variables for the EDE-Q7 subscales are change from Baseline to Week 12 in EDE-Q7 dietary restraint subscale score, change from Baseline to Week 12 in EDE-Q7 shape/weight overvaluation subscale score and change from Baseline to Week 12 in EDE-Q7 body dissatisfaction subscale scores.

- CGI-C score at Week 12. Missing assessments at Week 12 will be imputed using last on-treatment observation carried forward. Study participants with no on-treatment assessment will have a missing value. Additionally, improvement according to CGI-C is defined as CGI-C at Week 12 equal to "Much Improved" or "Very Much Improved". If CGI-C at Week 12 is missing, the study participant will be assumed to not have improved.
- PGI-C score at Week 12. Missing assessments at Week 12 will be imputed using last on-treatment observation carried forward. Study participants with no on-treatment assessment will have a missing value. Additionally, improvement according to PGI-C is defined as PGI-C at Week 12 equal to "Much Improved" or "Very Much Improved". If PGI-C at Week 12 is missing, study participant will be assumed to not have improved.
- Change from baseline to Week 12 in the CGI-S score, defined as the difference of CGI-S score at Week 12 and at Baseline. Missing assessments at Week 12 will be imputed using last on-treatment observation carried forward.
- Change from baseline to Week 12 in the PGI-S score, defined as the difference of PGI-S score at Week 12 and at Baseline. Missing assessments at Week 12 will be imputed using last on-treatment observation carried forward.

# 9.2.4.2 Analyses

Other efficacy endpoints will be tested at the two-sided 5% significance level. No further Type I error control is applied, so these analyses are to be considered descriptive.

# Change from baseline to Weeks 11-12 of the number of BE episodes per week

Changes from baseline to post-baseline time points will be analyzed using the same mixed model for repeated measurements as for the primary efficacy endpoint, only with a covariate for the baseline number of BE episodes (rather than the number of BE days) per week. Measurements obtained after premature treatment discontinuation will be excluded from the analysis [supplementary estimand #1, Table 4].

# Absence of BE episodes during the last 4 weeks of the treatment period

Absence of BE episodes will be analyzed using a logistic regression model with a factor for treatment group, sex and BMI category and a covariate for the baseline number of BE episodes per week. For study participants who discontinued treatment prematurely, the outcome will be set to 'No absence'.

# Change from baseline to Week 12 in EDE-Q7 global score and 3 subscales

Changes from baseline in EDE-Q7 scores will be analyzed using a mixed model for repeated measurements as described for the primary endpoint, but with less time points.

# CGI-C score at Week 12

CGI-C scores will be compared between treatment groups using the Kruskal Wallis test.

# Improvement according to CGI-C at Week 12

This variable will be analyzed using a logistic regression model with a factor for treatment group. The relationship between improvement according to CGI-C at Week 12 and the primary efficacy outcome will be investigated.

# PGI-C score at Week 12

This variable will be analyzed using same methods as for CGI-C score at Week 12.

# Change from baseline to Week 12 in the CGI-S score

Changes from baseline to Week 12 in CGI-S score will be analyzed in an analysis of covariance (ANCOVA) model with a factor for treatment group and a covariate for baseline score.

# Change from baseline to Week 12 in the PGI-S score

This variable will be analyzed using same methods as for change from baseline to Week 12 in the CGI-S score.

# 9.2.5 Analysis of safety outcomes

The SAF will be used to perform all safety analyses.

Unless otherwise stated, only treatment-emergent safety data will be considered in tables and figures. All safety data will be included in listings.

# 9.2.6 Adverse events

# 9.2.6.1.1. TEAEs and SAEs

TEAEs and SAEs, including AESIs, will be tabulated by study treatment, SOC, and preferred terms within each SOC: the number and percentage of study participants who experienced at least one (S)AE, at least one (S)AE within each SOC, and at least one (S)AE within each preferred term will be displayed. (S)AEs will also be summarized by decreasing frequency of preferred term. (S)AEs will also be tabulated by maximum intensity and by relationship to study treatment.

# 9.2.6.1.2. AEs leading to premature discontinuation of study treatment

AEs leading to premature discontinuation of study treatment will be summarized in a similar manner as that described in Section 9.2.6.1.1.

## 9.2.7 Laboratory data

## 9.2.7.1.1. Changes from baseline in laboratory variables

Descriptive summary statistics by visit and study treatment will be provided for observed treatment-emergent values as well as for changes from baseline for laboratory tests (hematology, blood chemistry, urinalysis).

Data will be displayed in SI units whenever possible and graphical approaches may be applied for certain variables.

#### 9.2.7.1.2. Treatment-emergent marked laboratory abnormalities

Laboratory abnormalities will be summarized descriptively by study treatment as categorical variables.

#### 9.2.8 Vital signs

Descriptive summary statistics by visit and study treatment will be provided for observed values and changes from baseline in pulse rate, respiratory rate, temperature, systolic and diastolic blood pressure, and body weight.

Notable blood pressure abnormalities will also be summarized descriptively.

# 9.2.9 Electrocardiography

Descriptive summary statistics by visit and study treatment will be provided for observed treatment-emergent values and changes from baseline in numeric 12-lead ECG values (HR, and the intervals PR, QRS, QT, QTcB, and QTcF).

Treatment-emergent marked abnormalities for 12-lead ECG variables will be summarized at all visits.

In addition, morphological ECG abnormalities that were not present before first study treatment intake (using data from the ECG provider) will be summarized.

# 9.2.10 Specific safety endpoints

*Daytime sleepiness* is defined daily as any score > 3 on the SSS after taking the morning dose. It will be collected on Days 1–14 and expressed as a number of days per week (as for the primary efficacy outcome). A minimum of 7 diary entries are required, otherwise the data will be considered missing. The mean number of days with daytime sleepiness per week will be summarized by treatment group.

The number (%) of study participants with *suicidal ideation and/or behavior* based on the C-SSRS© will be tabulated by visit and treatment group.

*Withdrawal effects* will be described summarizing changes from changes from Week 12/EOT to EOS in BWSQ and HAMD-17 by treatment group.

#### 9.2.11 Analyses of other outcomes

A full description of all other analyses will be provided in the SAP.

#### 9.3 Interim analyses

No interim analysis is planned for this study.

#### 9.4 Sample size

The sample size is based on the primary efficacy endpoint, change from baseline to Week 12 in the number of BE days per week.

In 2 studies using lisdexamfetamine in study participants with BED [McElroy 2016] the difference between lisdexamfetamine and placebo for this endpoint was -1.35 (SD = 1.6) and -1.66 (SD = 1.6) days per week. The corresponding effect size was 0.83 (95% CI: 0.60–1.05) and 0.97 (95% CI: 0.72–1.21), respectively. In the USA, lisdexamfetamine is categorized as a Schedule II medication. For this reason, a smaller effect size by ACT-539313 may still be considered clinically important if it has a better safety profile than lisdexamfetamine.

In an earlier study comparing topiramate to placebo in study participants with BED [McElroy 2007] the difference in the means of the changes from Baseline to Week 16 between topiramate and placebo was -1.0 with a common SD of 2.0, providing an effect size of 0.5 (95% CI: 0.3–0.7).

In a recent study with dasotraline, the LSmean reduction from Baseline in number of BE days per week was significantly greater for dasotraline vs placebo at Week 12 (-3.74 vs -2.75), for an effect size = 0.74 [McElroy 2020].

Based on the above, it is assumed that a treatment group difference of 1 BE day per week (corresponding to an effect size of 0.5 to 0.7, depending on the SD) is clinically meaningful.

The sample size is based on the power to detect a reduction of at least 1 BE day per week at Week 12 (with an SD of 1.6, this corresponds to an effect size of 0.65), between ACT-539313 and placebo, at a significance level of 5% two sided. Table 5 shows the sample size needed to detect a difference between placebo and ACT-539313 for different effect sizes.

	-	-		
Effect size	0.5	0.6	0.7	
Power				
90%	170	118	86	
80%	126	88	66	

Table 5Total sample size for 90% power

For a two-sided  $\alpha = 0.05$  and 1:1 randomization

The sample sizes reported in Table 5 are based on a t-test, but are also valid for a mixed model for repeated measures, retaining close to 90% (or 80%) power in the case of missing Week 11–12 data (up to 20%).

Table 6 shows the power to detect a difference between placebo and ACT-539313 for a sample size of 100–120 study participants.

Table 6Power for sample sizes of 100 and 120

Effect size	0.5	0.6	0.7
Sample size			
100	71%	85%	94%
120	78%	91%	97%

For a two-sided  $\alpha = 0.05$  and 1:1 randomization

Assuming a sample size of 120 study participants (60 participants per arm), the power achieved in any of the scenarios described above, will be at least equal to 78% ( $\alpha = 0.05$ , two-sided).

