### Interim analysis

No interim analysis is planned.

8

ACT-539313 Binge Eating Disorder Protocol ID-082A201 Final Version 3 4 May 2021, page 27/140

Confidential

Sample size
The sample size is based on the primary efficacy endpoint. It is anticipated that a treatment group difference of 1 BE day per week (corresponding to an effect size of 0.5 to 0.7, depending on the standard deviation [SD]) is clinically meaningful as demonstrated in recent studies.
The sample size needed for 90% power to detect an effect size of 0.6 is 120 participants (60 participants per arm). Such a sample size would also provide 78% power to detect a smaller effect size of 0.5.

The associated estimands [ICH 2020] are given in Section 9.2.

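### Protocol 9.4: effect size 0.65 should be 0.625, the tables are not the t-test values claimed for Table 5, and the 78% power floor needs limiting to complete data

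*Protocol*

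**What the plan says.** Protocol section 9.4 plans on a difference of 1 BE day per week, two-sided 5% significance and 1:1 allocation. It takes an SD of 1.6 and says "this corresponds to an effect size of 0.65". It treats effect sizes from 0.5 to 0.7 as clinically meaningful.

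Table 5 gives total sample sizes for effect sizes 0.5, 0.6 and 0.7: 170, 118 and 86 for 90% power, and 126, 88 and 66 for 80%. On method, the protocol states: "The sample sizes reported in Table 5 are based on a t-test". The same sentence claims, for a loss of no more than 20% at the last time point, that these sizes "are also valid for a mixed model for repeated measures, retaining close to 90% (or 80%) power in the case of missing" values.

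Table 6, which names no method, gives power of 71%, 85% and 94% for 100 participants and 78%, 91% and 97% for 120. The section then concludes that with 120 participants "the power achieved in any of the scenarios described above, will be at least equal to 78" per cent.

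The synopsis says: "The sample size needed for 90% power to detect an effect size of 0.6 is 120 participants". It continues: "Such a sample size would also provide 78% power to detect a smaller effect size of 0.5".

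**The concern.** A power section should be reproducible from the inputs it prints. Here the effect size does not follow from the stated difference and SD, and the method named for Table 5 does not produce Table 5. The synopsis and Table 5 also give different totals (120 and 118) for the same target.

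The closing floor carries no complete-data condition. Missing Week 11–12 values are to be expected: section 5.9 does not replace participants who stop, and section 9.2.2.2 drops measurements taken after premature treatment discontinuation. Since 0.5 is the low end of the range called meaningful, a reader weighing a null result could take 78% there as already allowing for dropout.

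**Working it through.** **Inputs.** Two-sided α = 0.05, 1:1 allocation, 120 participants (60 per arm), difference 1 day, SD 1.6, effect sizes d = 0.5, 0.6 and 0.7, and up to 20% missing (all Protocol 9.4).

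**Table 5, normal approximation.** n per arm = 2(1.960 + z)²/d², rounded up, with z = 1.2816 for 90% power and 0.8416 for 80%.

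- 90%: 21.015/0.25 = 84.06, so 85 per arm (total 170); 21.015/0.36 = 58.4, so 59 (118); 21.015/0.49 = 42.9, so 43 (86).
- 80%: 15.698/0.25 = 62.8, so 63 (126); 15.698/0.36 = 43.6, so 44 (88); 15.698/0.49 = 32.04, so 33 (66).

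All six printed cells are reproduced exactly. The t-test (noncentral t) totals are 172, 120 and 88 for 90% power and 128, 90 and 68 for 80%, which is 2 more in every cell. At the printed sizes, t-test power is 89.4–90.0% and 79.5–80.0%. The synopsis total of 120 at effect size 0.6 equals the t-test total.

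**Table 6.** Normal-approximation power = Φ(d√(n/2) − 1.960). For 60 per arm and d = 0.5: 0.5 × √30 = 2.739, and Φ(0.779) = 78.2%.

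| N | d | Printed | Normal | t-test |
|---|---|---|---|---|
| 100 | 0.5 | 71% | 70.5% | 69.7% |
| 100 | 0.6 | 85% | 85.1% | 84.4% |
| 100 | 0.7 | 94% | 93.8% | 93.4% |
| 120 | 0.5 | 78% | 78.2% | 77.5% |
| 120 | 0.6 | 91% | 90.8% | 90.3% |
| 120 | 0.7 | 97% | 97.0% | 96.7% |

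The normal approximation matches all six cells after rounding. The t-test misses four; the 78% and 97% cells would round the same way under either method.

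**Effect size.** 1/1.6 = 0.625. An effect size of 0.65 needs an SD of 1/0.65 = 1.54. An SD that prints as 1.6 lies between 1.55 and 1.65, giving 0.606 to 0.645, so rounding would explain 0.65 only at the extreme edge. With 120 participants, power at 0.625 is 92.4% (t-test) or 92.8% (normal). At 0.65 it would be 94.2% or 94.5%.

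**20% missing with 120 participants.** Counting only participants with Week 11–12 data, 60 × 0.8 = 48 per arm. For d = 0.5 (normal): 0.5 × √24 = 2.449, and Φ(0.489) = 68.8%.

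| d | Normal | t-test |
|---|---|---|
| 0.5 | 68.8% | 67.9% |
| 0.6 | 83.6% | 82.9% |
| 0.7 | 92.9% | 92.4% |

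These are approximate lower bounds, because the planned mixed model also uses earlier visits and covariates. The protocol gives neither visit correlations nor dropout timing, so a range was assumed: compound symmetry or AR(1), correlation 0.3 to 0.9, early, even or late monotone dropout, six visits and no covariate gain. Normal-approximation power at d = 0.5 then runs from 68.8% to 77.0%.

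If covariates remove a fraction g of the planning variance, n per arm acts like n/(1 − g). With g = 0.20, 48/0.80 = 60, so even the completers-only case returns to 78.2%.

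**The case against.** The strongest reply concerns the floor. The sentence opens by assuming 120 participants and comes straight after Table 6, whose 120-participant row has 78% as its minimum. The missing-data remark comes before that table and concerns the Table 5 sizes, none of which is 120. On that reading no scenario of 120 participants with 20% missing was ever described, and 78% is correct. This stands; what remains is an unstated condition.

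A reader might infer more: that the 20% assurance is wrong, or that true power at 0.5 is about 68%. The documents do not support either. The protocol claims only to stay close to nominal power. It names the model, including "covariates for baseline number of BE days per week and the interaction between baseline and time point", and says: "The primary efficacy analysis assumes a missing at random mechanism". The completers-only figure describes an analysis nobody plans, and the mixed-model range rests on assumed correlations and dropout. Whether covariates would add power depends on whether the planning SDs were already adjusted, which the documents do not say. Asking for the assumptions behind the assurance is a request for detail.

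On the tables, a gap of 2 participants per cell is immaterial to the design. The synopsis total of 120 may simply be 118 rounded up. On effect size, 0.65 enters neither table, and the synopsis ties 120 to 0.6. These replies limit the weight of the points but do not make the printed statements correct.

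**Conclusion.** Two items in section 9.4 do not follow from its own inputs, and a third needs a limit.

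- The effect size for 1 day and SD 1.6 is 0.625. Printing 0.65 overstates t-test power with 120 participants by 1.8 points (94.2% against 92.4%).
- Table 5 is not t-test based as stated. Both tables are normal-approximation values, and Table 5 runs 2 participants below the t-test in each cell.
- The 78% floor is right for complete data under the normal approximation (77.5% by t-test) but is worded without that condition.

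The 20% assurance is undocumented, not refuted. The complete-data figures rest only on the protocol's inputs; the mixed-model range rests on the assumptions stated with it. Severity is minor. At effect size 0.6 and above, even the completers-only bound with 20% missing is about 83% or more, and nothing here changes the sample size, analysis or decision rule.

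**What to change.** 1. Change 0.65 to 0.625.
2. Use one method throughout section 9.4 and the synopsis:
   - *Normal approximation:* label both tables and the 78% accordingly, and say in the synopsis that 118 are needed for 90% power at 0.6, with 120 giving 91%.
   - *t-test:* print 172/120/88 and 128/90/68 in Table 5, and 69.7/84.4/93.4% (N = 100) and 77.5/90.3/96.7% (N = 120) in Table 6. State the floor as 77.5% in both places.
3. Add to the closing sentence and the synopsis that the floor assumes complete Week 11–12 data.
4. If a figure for 20% missing is wanted, give the completers-only lower bound for 120 participants by the chosen method: 68.8/83.6/92.9% (normal) or 67.9/82.9/92.4% (t-test) at 0.5/0.6/0.7. Note that the mixed model and covariates may recover part or all of the loss. Alternatively, state the sponsor's own correlation, dropout and covariate assumptions with the resulting power.

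The cost is wording in section 9.4 and the synopsis. No participants are added, though the stated power under missing data may look less favourable.
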